Population: 10,449 patients aged 16-35 years in CPRD with TASD and two years follow up.

WP1: Internal and external validation of shoulder dislocation coding and treatments within a routinely collected dataset (CPRD).

WP2: Propensity score-matched cohort study using linked CPRD and HES. All events and outcomes will be collected using a pre-agreed list of READ CODES (CPRD) and OPCS 4.7 CODES (HES).

Exclusions: Surgery after more than one dislocation; instability treated with a rotator cuff repair or fracture surgery.

Intervention: Surgical repair within 6 months of first time T ASD.

Control: non-surgical intervention.

Outcomes: Rate of re-dislocation, identified by codes in CPRD for 2 years after either treatment.

Sample size: 3065 with 656 expected total number of re-dislocations (90% power, 5% significance).

Statistical analysis: Propensity scores, Cox regression modelling and Rosenbaum bounds sensitivity analysis for *Surgical versus non-surgical intervention on re-dislocation*. Multiple imputation methods, survival models and fractional polynomials for *Predictors of recurrent dislocations*.

C. Objectives, Specific Aims and Rationale

Aim 1. To study the association between surgical treatment (compared to no surgery) and recurrence rates following a first episode of traumatic anterior shoulder dislocation (T ASD) amongst young adults. **Aim 2.** To identify clinical predictors of further recurrent dislocations in young adults with traumatic anterior shoulder dislocation stratified by surgery and no surgery.

Objectives: Following the HTA commissioning brief, we plan to use routinely collected observational datasets (Clinical Practice Research Datalink (CPRD) and Hospital Episodes Statistics (HES)) to answer the research questions above. The size of routinely collected data in UK primary care (CPRD) and secondary care (HES) offers rapid observational data to uncertainties about treatments in an affordable and generalisable manner. We have planned a propensity score-matched cohort study, with the intention to minimise confounding. Propensity score matching is considered one of the best methods available to approximate to any results obtained from randomised controlled trials. To ensure further value for money and to confirm the ability of these datasets to answer this very specific commissioned question, we plan a two stage approach through Work Packages 1 and 2.

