Main study (WP2): The main study (WP2) will be a population based propensity score-matched cohort study using CPRD and HES collected datasets. The cohort of participants in this study will be young adults (aged 16–35 years) with traumatic anterior shoulder dislocation (T ASD) with at least 2 years data entry in CPRD before the their first shoulder dislocation code and at 2 years follow up from their first dislocation code entry in CPRD. All events and outcomes will be collected using a pre-agreed validated list of READ CODES (CPRD) and OPCS 4.7 CODES (HES). These codes are listed in the appendices and have already been identified. They will be further validated and informed by WP1. The first read code entry in CPRD for shoulder dislocation will be defined as the ‘first dislocation’. These codes will then be routinely linked to patients and to HES.

The ***Intervention group*** will be patients in CPRD with first time T ASD who underwent shoulder stabilisation surgery after their first dislocation (early surgical repair in this NHS context will mean ‘a decision to treat surgically after the first T ASD’ and receiving surgery within 6 months). This means linking HES data to CPRD data in such a way that a HES surgical OPCS 4.7 code is seen to occur after a single first dislocation code in CPRD (without further dislocation codes) before that surgical date. The timelines between first dislocation codes and OPCS 4.7 codes will be recorded. The ***Control group***. While the most desirable control group would be physiotherapy, it is possible that WP1 will reveal that free text notes and referral codes on physiotherapy will be lacking and not reliable. If this is the case then conservative care will be defined as ‘non surgical intervention’ with no linked OPCS 4.7 surgical shoulder codes producing a control cohort of patients whose first time shoulder dislocation has been treated non-operatively. If however free text entries and referral codes for physiotherapy are reliably present in CPRD then conservative care will be physiotherapy identified by physiotherapy referral codes after a first time T ASD code. Any subsequent dislocation codes or OPCS 4.7 surgery code will be recorded.

This project was funded by the National Institute for Health Research Health Technology Assessment (project number 14/160/01).

The views and opinions expressed therein are those of the authors and do not necessarily reflect those of the HTA, NIHR, NHS or the Department of Health.

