The ***Intervention group*** will be patients in CPRD with first time T ASD who underwent shoulder stabilisation surgery after their first dislocation (early surgical repair in this NHS context will mean 'a decision to treat surgically after the first T ASD' and receiving surgery within 6 months). This means linking HES data to CPRD data in such a way that a HES surgical OPCS 4.7 code is seen to occur after a single first dislocation code in CPRD (without further dislocation codes) before that surgical date. The timelines between first dislocation codes and OPCS 4.7 codes will be recorded. The ***Control group***. While the most desirable control group would be physiotherapy, it is possible that WP1 will reveal that free text notes and referral codes on physiotherapy will be lacking and not reliable. If this is the case then conservative care will be defined as 'non surgical intervention' with no linked OPCS 4.7 surgical shoulder codes producing a control cohort of patients whose first time shoulder dislocation has been treated non-operatively. If however free text entries and referral codes for physiotherapy are reliably present in CPRD then conservative care will be physiotherapy identified by physiotherapy referral codes after a first time T ASD code. Any subsequent dislocation codes or OPCS 4.7 surgery code will be recorded.

K. Exposures, Outcomes and Covariates

As part of this application, we have performed a consensus survey of specialist shoulder surgeons and shoulder physiotherapists who are all members of the British Elbow and Shoulder Society. Saturation point and a list of predictors was reached rapidly and this list is tabulated in Appendix E and highlights the risk factors (and covariates) deemed most important. It is unlikely that all of these will be available from routinely collected national datasets but our study design will allow us to confirm through WP1 those factors that are reliably collected and that can be used for full analysis in WP2.

L. Data/ Statistical analysis

The association of surgical versus non-surgical intervention on subsequent re-dislocation within 2-years. The primary outcome of interest is the time from a first time traumatic anterior dislocation to subsequent re-dislocation within 2-years. The exposure of interest is whether or not a patient received shoulder surgery. In randomized controlled trials each person has

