Matched surgical patients and their non-surgical controls will then be included in a Cox regression survival model to describe the association between receipt of surgery and time to subsequent dislocation within 2-years. The model is stratified on matched sets, to allow for the correlation between matched pairs of surgical patients and controls. As clustering exists within the data (patients nested within GP practices), a multilevel survival model will be fitted by extending the Cox regression model to include a frailty term with a Gaussian distribution[8]. This will allow adjustment for evidence of unexplained variation across GP practices. To assess the potential effect of unmeasured confounders we will conduct a Rosenbaum bounds sensitivity analysis[9]. This provides an estimate of the magnitude of hidden bias that would have to be present to explain the associations actually observed. The proportional hazards assumption will be assessed using Schoenfeld's residuals. Kaplan-Meier plots will be used to estimate the probability of survival up to 2-years in surgical and non-surgical groups.

Identifying predictors of recurrent dislocations

Using the CPRD-HES linked dataset we will develop a prediction model to identify patients at increased risk of subsequent re-dislocation. Potential risk factors will include all those described above. The cumulative effect of missing data in several variables often leads to exclusion of a substantial proportion of the original sample, causing a loss of precision and power. To overcome this bias we will use multiple imputation methods, which allows for the uncertainty about missing data by creating several plausible imputed datasets and appropriately combining their results [10, 11].

Survival models (Cox regression) will be used to identify risk factors associated with time to re-dislocation. Backward selection methods will be used to identify risk factors and shrinkage methods applied to adjust for over fitting. Continuous predictors will be examined using fractional polynomials and clinically plausible interaction terms will be tested for inclusion (specifically whether the predictors differ in the surgical and non-surgical intervention groups). For internal validation of the model we will use a combination of multiple imputation and bootstrapping[12-14].

Performance of the model will be assessed in terms of calibration and discrimination[11, 23]

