APPENDIX E

Table of Expert Consensus List of Risk Factors.

Risk factors for re-dislocation after first dislocation	Risk factors for re- dislocation after surgery
Age	Age
Gender	Gender
UK Region	UK Region
Deprivation Scores	Deprivation Scores
Glenoid and / or Humeral Bone loss	Glenoid and / or Humeral Bone loss
Mechanism of injury	Number of dislocations pre-surgical repair
Rotator cuff tears	Time between first dislocation and surgery
Imaging findings	Anterior apprehension
Anterior apprehension	Occupation
Occupation	Sport type and level
Sport type and level	Operation type
Neurological injury	Laxity/Beighton Score
Laxity/Beighton Score	Insufficient physio / rehab after surgery
Insufficient physio / rehab after first dislocation	Time for return to sports
Young Rugby player under 20	Number of anchors used at surgery
Time at return to sports	Incorrect positioning of anchors
Post dislocation immobilisation	Not addressing capsular laxity at surgery
	Previous lower limb or back injury

This project was funded by the National Institute for Health Research Health Technology Assessment (project number 14/160/01).

The views and opinions expressed therein are those of the authors and do not necessarily reflect those of the HTA, NIHR, NHS or the Department of Health.

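### The protocol conflicts on the outcome clock and gives the Aim 2 model no time origin; on section L's first-dislocation clock, waiting time to surgery would be a biased predictor in operated patients

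*Protocol*

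**What the plan says.** - **Aim 2 (section C):** "To identify clinical predictors of further recurrent dislocations in young adults with traumatic anterior shoulder dislocation stratified by surgery and no surgery".
- **Aim 2 model (section L, predictors of recurrent dislocation):** "Survival models (Cox regression) will be used to identify risk factors associated with time to re-dislocation", with no time origin. On candidates: "Potential risk factors will include all those described above". Backward selection, shrinkage and predictor-by-surgery interactions follow.
- **Appendix E, column on risk factors after surgery:** "Time between first dislocation and surgery" is listed. Sections F and J say the interval between the dislocation code and the surgical code will be recorded.
- **Clock in section L (under the surgical versus non-surgical heading):** "The primary outcome of interest is the time from a first time traumatic anterior dislocation to subsequent re-dislocation within 2-years". Section F anchors cohort follow-up at the same point: "at 2 years follow up from their first dislocation code entry in CPRD".
- **Clock in section B (Technical Summary):** "Rate of re-dislocation, identified by codes in CPRD for 2 years after either treatment".
- **Definition of the operated group (sections F and J):** surgery falls within 6 months, and the surgical code "is seen to occur after a single first dislocation code in CPRD (without further dislocation codes) before that surgical date". Section I excludes surgery after more than one dislocation.
- **Immortal time (section L):** for the surgery group, time before surgery is reclassified as non-surgical. This is set out just before the matched Cox model and is not repeated for Aim 2.

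**The concern.** An operated patient cannot have a counted event before surgery, because an earlier re-dislocation would remove that patient from the operated group. On a clock that starts at first dislocation and stops at 2 years, a patient operated on at month 6 is event-free for 6 months by definition and has 18 months at risk. One operated on at month 1 has 23 months at risk. The length of the guaranteed event-free period is the candidate predictor itself.

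This is the immortal-time problem that section L describes for the treatment comparison, now inside a prediction model. At stake are the coefficient for waiting time and any predicted risk for operated patients that readers take as risk after surgery. Bootstrap validation would not reveal the problem, since every resample carries the same artefact.

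**Working it through.** **1. The plan's own figure.** The protocol gives a sample size for Aim 1 only (section G).
- Hazard ratio = ln(0.80)/ln(0.75) = 0.7757, stated as 0.78.
- With exponential loss of 10% over 2 years, λ = −ln(1−p)/2 and e = −ln(0.9)/2. Then P(event) = λ/(λ+e) × [1 − exp(−2(λ+e))] = 0.2379 (non-surgical) and 0.1902 (surgical), mean 0.2140.
- 3065 × 0.2140 = 656 events, and 656 events give 90.2% power. The stated figures reproduce. There is no figure for Aim 2.

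**2. Inputs for the Aim 2 check.**
- From the protocol: 20% two-year risk in the surgical group, surgery within 6 months, no event before surgery, and a 24-month limit from first dislocation.
- Assumed: 1,533 operated patients (3065/2); waits uniform over 0-6 months; a Weibull hazard after surgery with shape 0.6 (falling), 1.0 (constant) or 1.5 (rising); no effect of waiting.

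**3. Risk by hand, constant hazard.** Monthly hazard h = −ln(0.80)/24. Risk to 24 months from dislocation after a wait of w months is 1 − exp(−h(24−w)).
- w = 0: 20.0%; w = 3: 17.7%; w = 6: 15.4%.
- Mean over uniform waits: 17.7%, against 20.0% over 24 months after surgery.
- Ratio of cumulative hazards, 6-month wait against none: 18/24 = 0.75. This is roughly the spurious hazard ratio to expect per 6 months.

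**4. Cox model with waiting time as covariate (400 runs per hazard shape; the true hazard ratio is 1).** Hazard ratios are per 6 months' later surgery; false rejection at 5% is in brackets.

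| Hazard after surgery | Dislocation clock | Dislocation clock, late entry at surgery | Surgery clock | Risk seen on dislocation clock |
|---|---|---|---|---|
| Constant (1.0) | 0.73 (34%) | 1.00 (5%) | 0.99 (4%) | 17.7% |
| Falling (0.6) | 0.80 (21%) | 1.90 (79%) | 0.99 (4%) | 18.6% |
| Rising (1.5) | 0.64 (52%) | 0.71 (31%) | 1.01 (3%) | 16.7% |

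Repeat runs agree closely on the dislocation clock: 0.74 for constant hazard and 0.65 to 0.80 across shapes. With waits uniform over 3-6 months the hazard ratios are similar (0.63 to 0.79), but false rejection falls to 7-19% because waits vary less.

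**5. Why late entry is not enough.** Late entry removes the event-free time. At a given time since dislocation, however, it still compares patients at different times since surgery. If the hazard falls after surgery, the later-operated patient sits higher on that curve and waiting looks harmful. If it rises, waiting looks protective. Only a constant hazard makes this harmless.

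**6. Surgery clock with the follow-up actually guaranteed.** The surgery-clock column above uses a full 24 months after surgery. With censoring at 24 months from dislocation, so 18-24 months after surgery, simulations over other wait patterns and shapes 0.7 and 1.0 give hazard ratios of 0.990-1.003 per month and 2-5% rejection.

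**The case against.** The strongest reply is that the protocol does not fix the biased analysis. A reader might infer that Aim 2 counts time from the first dislocation. The Aim 2 text gives no origin, section L's definition stands under the Aim 1 heading, and both section B and the title of the Appendix E column point towards a clock after surgery. That part stands, so the bias is conditional on which clock is used. The conflict between the clocks remains and needs settling.

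The immortal-time rule is worded for the study generally and could be read as covering Aim 2. In the operated stratum it would then act as late entry. This stands for constant hazard only; under the other assumed shapes the coefficient is biased upwards or downwards.

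A reader might also infer that the model will report later surgery as protective. The documents do not support that. Appendix E is an expert list, and section K expects that some items will be unavailable. The same column includes the number of dislocations before repair, which is constant here given the exclusions. Waiting time must still pass backward selection, for which no threshold is stated, and at 34% false rejection a 5% rule would often drop it. Section L also describes one model with interactions and no separate operated-only model.

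Finally, 17.7% is not a wrong number. It is the correct risk to 2 years from dislocation, and it understates only if labelled as risk over 2 years after surgery.

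One might leave all this to the updated analysis plan promised in section F before WP2. That is a fair place for the correction, but the conflicting clocks and the listed predictor are already in the protocol.

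**Conclusion.** The point holds in conditional form. The protocol states two clocks, gives none for Aim 2, and lists a predictor whose meaning depends on the choice. On section L's clock without late entry, the spurious hazard ratio is about 0.73-0.74 per 6 months' later surgery for constant hazard, and 0.64 to 0.80 across the assumed shapes. A 20% post-surgery risk appears as about 17.7% (16.7% to 18.6%). The distortion in risk is bounded by the 6-month window: for constant hazard it is 2.3 points on average (20.0 − 17.7) and 4.6 at most (20.0 − 15.4).

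The hazard shapes, wait pattern and number of operated patients are assumptions. The direction on the uncorrected dislocation clock was the same in every scenario, while the false-rejection rate depends strongly on the spread of waits and on sample size. This concerns the second aim and does not touch the Aim 1 sample size, which reproduces. The correction should be made.

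**What to change.** In section L, or in the updated analysis plan before WP2:
- For Aim 2 in operated patients, set the time origin at the date of surgery, with waiting time as a covariate known at that origin.
- Censor at the end of available follow-up (18-24 months after surgery is guaranteed), and report predicted risk at a horizon measured from surgery.
- Fit waiting time only within the surgical stratum. Keep the dislocation clock for the non-surgical stratum.
- Do not test predictor-by-surgery interactions by pooling the two clocks; set the stratum-specific estimates side by side.
- Do not rely on late entry on the dislocation clock as the remedy.
- Reconcile the outcome window in section B with sections F and L, and state the origin in the Aim 2 text.

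The cost is a few sentences and a changed origin in the survival set-up. Some operated patients will be censored before 24 months after surgery, and the pooled interaction test is given up.

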Using data from a Cochrane systematic review comparing surgical to non-surgical treatment for acute T ASD [6]; from the pooled results 3/58 patients in the surgical arm had subsequent further surgery (5.17%) compared to 17/61 in the non-surgical arm (27.9%) at a minimum follow up of 2-years (Risk Ratio 0.22, 95% CI 0.08 to 0.64). The large effect size is set in the context of the pooled results of 3 RCTs with uncertainty around the true size of the effect outside of a clinical trial setting in routine general practice. Conservatively, we would look to detect a smaller difference in subsequent surgery within 2-years of 25% in the non-surgical group, compared to 20% in the surgical group (an absolute difference of 5%). A 2-sided log rank test for equality of survival curves, with 90% power at 5% significance level (alpha), where outcome is time to re-dislocation, with an anticipated 25% re-dislocation rate in the non-surgical control group compared to a 20% in the surgical group (equivalent to a hazard ratio of 0.78), allowing for 10% loss to follow up and assuming equal group sizes, we require a total sample size of 3065 with 656 expected total of re-dislocations. There are 26,534 patients in CPRD with recurrent anterior shoulder dislocations, and at least 10,449 of these patients will be aged 16-35 years with T ASD [7]. The study will therefore be adequately powered. ***See flow diagram in appendix for estimation of numbers.***

H. Data Linkage Required (if applicable)

Data linkage and data management for our proposed study involves 2 different data sources (CPRD and HES). They need to be linked to answer the aims of WP2 as stated above. We have therefore included co-applicants with extensive experience in the use of linked datasets. The data management needed to produce a final working dataset will be carried out by a senior data manager at Oxford with expertise in such procedures. Under supervision from the application team, the data manager will develop ad-hoc code in Python and SQL to produce a dataset that can be analysed using standard statistical packages such as Stata.

I. Study Population

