This project was funded by the National Institute for Health Research Health Technology Assessment (project number 14/160/01).

The views and opinions expressed therein are those of the authors and do not necessarily reflect those of the HTA, NIHR, NHS or the Department of Health.

an equal probability of being in a treatment or control group. Observational study designs are limited by an inherent imbalance of both known and unknown confounders making some patients more likely to receive surgery than others. As the type of surgery received is not randomly allocated in our study, confounding by indication will be accounted for by using propensity score matching methods. Use of these methods for the assessment of causality in epidemiological studies has been previously described[1]. The propensity score represents the probability that a patient received the intervention (surgery). A logistic equation is fitted where the outcome is surgical intervention versus non-surgical; and any covariates are introduced as potential confounders of subsequent dislocation. We have already identified an expert consensus list of all potential confounders of interest (Appendix E)

Propensity scores are used to match each patient receiving surgery to comparable non-surgical controls using a caliper width of 0.2 standard deviations of the logit of the propensity score[2]. This is a standard method for minimizing confounding by indication, which not only balances observed baseline characteristics in both surgical and non-surgical groups, but also eliminates surgical patients with no comparable controls[3].

Immortal time bias is a common issue in epidemiological studies, where the event of interest cannot occur for a certain time span. In the case of this proposed study immortal time bias would occur due to the definition of exposure, where in the time from first dislocation till receipt of surgery those in the 'surgical arm' cannot have the outcome by design otherwise they would have been classified as non-surgical. To avoid the problem of immortal time bias, we will use time varying exposures, where in a survival analysis the time period previous to the index date of surgery is reclassified as non-surgical for those in the surgical intervention group.

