Calibration measures how closely predicted risk agrees with observed outcomes, which will

This project was funded by the National Institute for Health Research Health Technology Assessment (project number 14/160/01).

The views and opinions expressed therein are those of the authors and do not necessarily reflect those of the HTA, NIHR, NHS or the Department of Health.

be assessed graphically and quantified by estimating the calibration slope and intercept. Discrimination is the ability of the model to differentiate between people who have a re-dislocation versus those who don't. Discrimination will be assessed by calculating the area under the ROC curve, or the equivalent concordance (C) index.

Sensitivity Analysis:

In order to minimise Berkson's bias in the analysis of the association between surgical repair and re-dislocation, we will explore the hazard function for both exposed (i.e. those undergoing surgery) and unexposed participants. If this suggests such a bias, then we will run a sensitivity analysis excluding patients with early re-dislocation following surgery, which is a very uncommon event.

M. Plan for addressing confounding

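### The conditional Berkson sensitivity analysis drops surgical patients for having the primary outcome early, with no matching rule for controls, so that estimate shifts toward surgery

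*Protocol*

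**What the plan says.** Section L of the protocol ends with a short paragraph headed Sensitivity Analysis. Its stated purpose is given as "In order to minimise Berkson's bias in the analysis of the association between surgical repair and re-dislocation". The first step is a diagnostic: "we will explore the hazard function for both exposed (i.e. those undergoing surgery) and unexposed participants". The second step depends on the first. If the diagnostic points to such a bias, "we will run a sensitivity analysis excluding patients with early re-dislocation following surgery, which is a very uncommon event".

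Three other statements in section L bear on this:

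- The event used to exclude patients is the study endpoint: "The primary outcome of interest is the time from a first time traumatic anterior dislocation to subsequent re-dislocation within 2-years".
- Time between first dislocation and surgery is already dealt with through a time-varying exposure, under which "the time period previous to the index date of surgery is reclassified as non-surgical".
- The Cox model compares within matched sets: "The model is stratified on matched sets, to allow for the correlation between matched pairs of surgical patients and controls".

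No section states a parallel exclusion of early re-dislocations among non-surgical patients.

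**The concern.** A patient can re-dislocate after surgery only by having had surgery, so the exclusion works in one group. It also selects on the primary outcome. The people removed are surgical patients whose operation failed early, and those failures occur after the surgery date, so the time-varying exposure correctly attributes them to surgery. Controls who re-dislocate equally early stay in.

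This is selection on the outcome within one exposure group. It introduces a selection bias of its own and does not correct Berkson's bias. A sensitivity analysis is read as a test of whether the main conclusion survives. If the primary analysis finds a benefit of surgery, an analysis that has removed part of the evidence against surgery can be expected to agree, and a reader could mistake that agreement for support. Section Q says that the results are meant to inform updated guidelines.

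**Working it through.** **Inputs (protocol, section G).** The design is "A 2-sided log rank test for equality of survival curves, with 90% power at 5% significance level (alpha"). Its assumed risks are "anticipated 25% re-dislocation rate in the non-surgical control group compared to a 20% in the surgical group (equivalent to a hazard ratio of 0.78"), together with equal groups, 10% loss, 3065 patients and 656 events.

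**Reproducing the baseline.**
- Hazard ratio: ln(0.80)/ln(0.75) = 0.7757, the stated 0.78.
- Events: 652 by the Schoenfeld formula and 659 by the Freedman formula, on either side of the stated 656.
- Sample size: with 10% exponential loss over two years the mean event probability is 0.2140, and 656/0.2140 = 3065, as stated.

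The planning figures are sound and serve as the starting point.

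**Effect of the one-sided deletion.** Let p be the surgical two-year risk and e the share of surgical patients deleted for early failure. Controls stay at 25%.

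- Surgical risk after deletion: p′ = (p − e)/(1 − e)
- Hazard ratio: HR = ln(1 − p′)/ln(0.75)
- Patients deleted: e × 3065/2 = e × 1532.5

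The protocol gives no value for e, so a range is shown.

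| e (points) | Patients deleted | p′, planned p = 20% | HR | p′, no effect p = 25% | HR |
|---|---|---|---|---|---|
| 0 | 0 | 0.2000 | 0.776 | 0.2500 | 1.000 |
| 0.5 | 7.7 | 0.1960 | 0.758 | 0.2462 | 0.983 |
| 1 | 15.3 | 0.1919 | 0.741 | 0.2424 | 0.965 |
| 2 | 30.7 | 0.1837 | 0.705 | 0.2347 | 0.930 |

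At the planned risk, 1 and 2 points are 5% and 10% of surgical events (1/20 and 2/20).

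**Chance of a nominally significant result for surgery when there is no effect.** This is approximately Φ(√(E/4) × (−ln HR) − 1.96), with E = 1532.5 × (0.50 − e), ignoring loss to follow-up.
- e = 1 point: E = 751; 13.70 × 0.0356 − 1.96 = −1.47, so about 7%.
- e = 2 points: E = 736; 13.56 × 0.0728 − 1.96 = −0.97, so about 17%.
- With no deletion it is 2.5%.

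**Does stratifying on matched sets help?** No. Once the surgical member is deleted, the rest of the set is all unexposed and tells the model nothing about surgery. With 1:1 pairs the stratified estimate is essentially the number of pairs in which the surgical patient fails first, divided by the number in which the control fails first. The rule removes mainly pairs from the numerator.

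**Does a symmetric rule help?** A simulation with unmatched groups of 1,532, constant hazard, 24 months and 2,000 runs was used, with the early window as an assumption:
- Deleting surgical failures in the first month only: HR 0.954 under no effect (about 18 patients deleted) and 0.740 under the planned effect, in line with the table.
- A 3-month window in the surgical group only: 0.861 and 0.668.
- The same 3-month window in both groups: 0.998 and 0.775.

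The distortion comes from the one-sidedness, and symmetry removes it.

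**The case against.** The strongest reply concerns scope. This is one conditional sensitivity analysis. A reader might infer that the study's main result is biased toward surgery, but the documents do not support that: the primary analysis in section L keeps every post-surgical re-dislocation, and nothing in the protocol makes a conclusion depend on the sensitivity estimate. This part of the reply stands in full.

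A second tempting inference is that the analysis must always look favourable to surgery and can test nothing. That also goes too far. The direction of the shift is fixed, but the resulting estimate need not favour surgery. If the primary result is null or shows harm, and remains so after early surgical failures are removed, the conclusion has survived a bound tilted toward surgery. The analysis fails only as confirmation of a benefit.

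Third, large shifts can be generated. Deleting 5 points gives 0.597 under the planned effect and 0.82 under no effect, but that removes about 77 of 306 planned surgical events, a quarter of them, which does not fit an event that the protocol calls very uncommon. The simulated 3-month window likewise makes early events common through its constant hazard, so it illustrates the mechanism and does not forecast the size.

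A substantive defence is also possible: early dislocation codes may be reviews of the first episode, a worry set out in the GP questionnaire (Appendix I). Section L does not give that reason, and miscoding of this kind could affect both groups, so it would call for the same rule in both.

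Inspecting hazards in both groups before a follow-up analysis is ordinary practice. The trigger threshold and the meaning of 'early' may sit in the analysis plan. Neither is counted here.

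**Conclusion.** The point holds for this sensitivity estimate only. As written, the rule excludes patients on the primary outcome in one group, and neither the time-varying exposure nor the matched-set stratification undoes the asymmetry. Agreement between this analysis and a primary finding of benefit would not show robustness.

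On the protocol's own premise of rarity, the size is modest: roughly 0.02 to 0.07 on the hazard ratio for deletions of 0.5 to 2 points. This rests on the planned risks in section G, on assumed values of e, and on two-year risks converted under proportional hazards. If early failures turn out to be less rare, the shift grows in the same direction. If they are rarer still, the analysis changes little and tests little.

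**What to change.** Replace the one-sided exclusion with a symmetric landmark analysis:

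1. Give each matched control an index date at the same time since first dislocation as its partner's surgery.
2. Start both members of the pair at the same lag after that date, with the lag fixed before outcome data are analysed.
3. Keep only pairs in which both members are event-free and under follow-up at the landmark.
4. Fit the same Cox model stratified on matched sets.
5. Report it beside the primary analysis, which keeps all early post-surgical re-dislocations, and state that it estimates the effect conditional on being event-free at the landmark.

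**Cost.** The data and model are unchanged, but this is more than a wording change. The protocol gives controls no surgery date, so the assigned index date is a new element to define. Some pairs are lost. If 1% of each group re-dislocates between index date and landmark, independently within pairs, 1 − 0.99² = 2.0% of pairs go (about 30 of 1,532). At 2% it is 1 − 0.98² = 4.0% (about 61). Pairs whose control re-dislocated before the index date also go, but with 1:1 matching these say nothing about surgery in the primary stratified model either, because both members are unexposed at that time. The landmark analysis also sets aside early surgical failures, which is why it must stand beside the primary analysis and not replace it.
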